### **Dose Escalation of GS-5829 and enzalutamide**

The first 3-4 subjects to enroll will receive GS-5829 at a dose level less than or equal to the previously determined MTD (or a monotherapy dose that has been determined to be safe), combined with enzalutamide. Enzalutamide is a strong CYP3A4 inducer, which is expected to decrease the exposure of GS-5829 and therefore a higher dose of GS-5829 may be required to achieve target coverage compared to the single agent dose. Subjects will administer enzalutamide 160 mg once daily as a single agent starting on Study Day 1 through Cycle 1 Day 1. On Cycle 1 Day 1 (approximately 14 days after Study Day 1), subjects will administer GS-5829 once daily in combination with enzalutamide 160 mg once daily in order to evaluate the interaction of the 2 agents. Depending on the observed PK interaction, toxicity and tolerability observed in the single agent dose escalation, the dose escalation may continue beyond a dose which has been identified to be safe and tolerable in the single agent arm. Any increase in the dose of GS-5829 will not be more than 100% in the next cohort.

Similar to the single agent dose escalation, the available safety, tolerability and PK data for each combination therapy cohort will be assessed by an SRT after all subjects in the cohort have been followed for at least 28 days after the first dose of GS-5829. If no DLTs occur in 3-4 subjects or

< 2 DLTs occur in up to 6 subjects on the first dose level after 28 days on treatment (C1D28), the second dose level will open. Each subsequent dose level will open if the dose level preceding has no DLTs in 3-4 subjects or < 2 DLTs in up to 6 subjects. The dose escalation intended is similar to that of the single agent GS-5829 (see [Table 3-1](#)). Depending on the exposure observed, the data (including PK, tolerability, safety and PSA response) will be evaluated to determine the appropriate GS-5829 dose in combination with enzalutamide. The dose of GS-5829 for the next combination therapy cohort will be communicated to the sites by administrative letter.

If a subject is enrolled in a cohort but does not complete the PK or PD analysis in the first 28 days of GS-5829 dosing, they may continue on study but an additional subject may be enrolled at that dose level.

The MTD of the combination therapy is the highest dose level with a subject incidence of 0 DLTs in 3-4 subjects or < 2 DLTs in 6 subjects during the first 28 days of study drug dosing. A minimum of 3 subjects need to be treated at a dose level before this dose level can be deemed as the MTD. Based on tolerability, PK, PD, efficacy and emerging data from other studies using GS-5829, dose escalation may be discontinued prior to reaching the MTD.

### **Dose Limiting Toxicity Definition**

A DLT is a toxicity defined below, considered possibly related to GS-5829, occurring during the DLT assessment window (Day 1 through Day 28) in each cohort:

- Grade  $\geq 4$  neutropenia (absolute neutrophil count [ANC]  $< 500/\text{mm}^3$ )
- Grade  $\geq 3$  neutropenia (ANC  $< 1000/\text{mm}^3$ ) with fever (a single temperature of  $> 38.3^\circ\text{C}$  or a sustained temperature of  $\geq 38^\circ\text{C}$  for more than one hour)
- Grade  $\geq 3$  thrombocytopenia
- Grade  $\geq 2$  bleeding (e.g. gastrointestinal, respiratory, epistaxis, purpura)
- Grade  $\geq 3$  or higher non-hematologic toxicity, except:
  - Grade 3 nausea or emesis with maximum duration of 48 hours on adequate medical therapy
  - Grade 3 diarrhea which persists for  $< 72$  hours in the absence of maximal medical therapy
- Grade  $\geq 2$  non-hematologic treatment-emergent adverse event (TEAE) that in the opinion of the investigator is of potential clinical significance such that further dose escalation would expose subjects to unacceptable risk
- Treatment interruption of  $\geq 7$  days due to unresolved toxicity

For certain toxicities, such as laboratory assessments without a clear clinical correlate, a discussion between the investigator and medical monitor may take place to determine if this adverse event (AE) should be assessed as a DLT necessitating dose reduction. However, any Grade 3 or Grade 4 elevation in AST or ALT associated with a Grade 2 elevation in bilirubin that is at least possibly related to study drug will be considered a DLT.

**Phase 2 Dose Expansion:**

Group 1: A dose that is less than or equal to the MTD of GS-5829 monotherapy (based on safety, PD and tolerability) will be chosen for the expansion phase. Approximately 20 subjects with mCRPC who have had radiographic disease progression despite adequate testosterone suppression and treatment with enzalutamide will be enrolled. These subjects may have previously received abiraterone. Enrollment into this group may initiate as soon as the MTD of single agent GS-5829 has been identified.

Group 2: A dose that is less than or equal to the MTD of GS-5829 + enzalutamide (based on safety, PD and tolerability) will be chosen for the expansion phase. Approximately 20 subjects with mCRPC who have had radiographic disease progression despite adequate testosterone suppression and treatment with abiraterone will be enrolled. These subjects may have previously received enzalutamide. Enzalutamide will be initiated on Study Day 1 and GS-5829 will initiate on Cycle 1, Day 1.

[figure not shown]
Group 3: A dose equivalent to the dose chosen for Group 2 will be chosen for an expansion phase. A maximum of 20 subjects with mCRPC who have had PSA only progression, but not radiographic progression, despite adequate testosterone suppression and treatment with enzalutamide will be enrolled. These subjects may have received prior abiraterone (similar to Group 1). These subjects will continue on the enzalutamide therapy they have been receiving (must be receiving continuous enzalutamide for at least 12 weeks prior to Cycle 1, Day 1) and GS-5829 will initiate on Cycle 1, Day 1) and GS-5829 will initiate on Cycle 1, Day 1.

The choice of enrolling a subject into a specific dose escalation cohort or dose expansion group will be based on the treatment slots open at the time of screening, inclusion/exclusion enrollment criteria and the discretion of the investigator.

### 3.2.1. Study Schema

Figure 3-1 provides the study schema

### Figure 3-1. Study Design and Treatment Schema

### Phase 2 – DOSE EXPANSION

- Dose expansion will begin after completion of the corresponding dose-escalation phase treatment
  - Group 1: GS-5829
  - Group 2: GS-5829 + enzalutamide
  - Group 3: GS-5829 + enzalutamide
- Dose level based upon results from the dose-escalation phase
- Up to 20 additional subjects in each arm

### 3.3. Study Treatments

Subjects who meet eligibility criteria will receive GS-5829 as a single agent or combined with enzalutamide orally once daily. Each cycle will consist of 28 days. Safety and efficacy assessments will occur on an outpatient basis including assessment of tumor response, physical exam, vitals, electrocardiogram (ECG), collection of blood samples (for routine safety labs, GS-5829 PK, PD markers, and biomarkers at applicable visits), and assessment of AEs. In addition, subjects will undergo a bone scan and CT (or MRI) every 12 weeks.

A subject who does not show evidence of disease progression may continue receiving GS-5829 as a single agent or combined with enzalutamide once daily until disease progression (clinical or radiographic), unacceptable toxicity, withdrawal of consent, or other reasons specified in Section 3.4. Subjects who have progressive disease by PSA measurements alone may continue study drug.

Following treatment, subjects will be followed for safety for 30 days and for survival.

### 3.4. Criteria for Discontinuation of Study Drug

Study medication may be discontinued in the following instances:

- Documented progression of malignant disease
- Death
- Investigator discretion
- Non-compliance with study drug
- Important protocol deviation

- Subject decision
- Lost to follow-up
- Study termination by the sponsor
- Intercurrent illness that would, in the judgment of the investigator, affect assessments of clinical status to a significant degree
- Unacceptable toxicity, as defined in the toxicity management section of the protocol, or toxicity that, in the judgment of the investigator, compromises the ability to continue study-specific procedures or is considered to not be in the subject's best interest

### **3.5. Criteria for Removal from Study**

Subjects may be removed from the study for the following reasons:

- Documented progression of malignant disease
- Death
- Investigator discretion
- Non-compliance with study drug
- Subject never dosed with study drug
- Important protocol deviation
- Withdrawal of consent
- Lost to follow-up
- Study termination by the sponsor
- Intercurrent illness that would, in the judgment of the investigator, affect assessments of clinical status to a significant degree
- Unacceptable toxicity, as defined in the toxicity management section of the protocol, or toxicity that, in the judgment of the investigator, compromises the ability to continue study-specific procedures or is considered to not be in the subject's best interest

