## **6.6. Post-Treatment 30-Day Safety Follow-up Visit**

All subjects will complete the 30-Day Safety Follow-Up visit. For Phase 1b Dose Escalation subjects, the 30-Day Safety Follow-Up will be the final study visit. Phase 2 Dose Expansion subjects will complete the 30-Day Safety Follow-Up Visit and proceed to Long Term Survival Follow-Up.

The following procedures will be completed 30 days after the subject's last dose of IP, within a window of  $\pm$  7 days:

- Physical examination, including weight
- Vital signs
- ECOG performance status
- Laboratory assessments
  - Chemistry
  - CBC with differential
  - Urinalysis
- Concomitant medications review
- Record any adverse events (30 days post last dose of IP)

For subjects who come off study treatment for reasons other than disease progression, the Investigator should also obtain information on the subject's post-study anti-cancer therapies, surgeries, and date of definitive disease progression (if known).

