## **6.7. Long Term Survival Follow-Up**

Phase 2 Dose Expansion subjects will participate in long term survival follow-up. These subjects will be contacted via phone call every 3 months for determination of long term survival status and record of any other anti-cancer therapy for up to 2 years after the last dose of IP. For subjects who discontinued the study for reasons other than disease progression, the Investigator should obtain information on the subject's post-study anti-cancer therapies, surgeries, and date of definitive disease progression (if known).

Subjects who are alive at the time the sponsor has made the determination the study will be ended will receive a final follow-up phone call to assess survival status and communicate the sponsor's decision. These subjects will be censored on the date the subject was last contacted.

The investigator will make every effort to contact the subject or a close relative or caretaker by phone to collect survival information. The investigator should show due diligence by documenting in the source documents steps taken to contact the subject i.e., dates of phone calls, registered letters, etc.

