## **6.10.          Post Study Care**

If a subject has discontinued the study treatment due to toxicity, he/she should not have withdrawal of consent recorded as the reason for discontinuation. Instead, the reason for discontinuation must be recorded as due to adverse event.

Every attempt should be made to keep the subject in the study and continue collecting CT or MRI scans for tumor assessment at every 12 weeks until disease progression or initiation of systemic anti-tumor therapy other than treatment per protocol. If this is not possible or acceptable to the subject or investigator, the subject may be withdrawn from the study. The subject will be asked to attend the post-treatment follow-up assessment visit above when discontinuing from the study treatment.

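### Protocol 3.5 permits removal from the study for nine of the ten reasons that stop study drug, in conflict with the planned survival and scan follow-up; for phase 1b the live conflict is the final 30-day visit

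*Protocol*

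**What the plan says.** Protocol 3.4 opens its list of ten drug-stopping reasons with "Study medication may be discontinued in the following instances". Section 3.5 gives eleven reasons for leaving the study, under "Subjects may be removed from the study for the following reasons". Its list includes "Documented progression of malignant disease" and "Unacceptable toxicity, as defined in the toxicity management section of the protocol".

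Four other sections set out what happens after treatment:

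- Section 3.3: "Following treatment, subjects will be followed for safety for 30 days and for survival". No exception is made for progression, toxicity or study phase.
- Section 6.7, for phase 2 subjects: "These subjects will be contacted via phone call every 3 months for determination of long term survival status", for up to 2 years after the last dose.
- Section 6.10, directly after a paragraph on subjects who stop for toxicity: "Every attempt should be made to keep the subject in the study and continue collecting CT or MRI scans for tumor assessment". Scans are to continue every 12 weeks until progression or a new systemic anti-tumor therapy.
- Section 6.6: "For Phase 1b Dose Escalation subjects, the 30-Day Safety Follow-Up will be the final study visit". Footnote 18 of the schedules in Protocol Appendices 2 and 3 and SAP Appendix 1 says the same.

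Protocol 8.1.3 makes PFS a secondary endpoint in both phases and OS a phase 2 endpoint. SAP 6.1.2 and 6.2.2 plan Kaplan-Meier estimates of PFS and OS at 24 and 48 weeks on the Full Analysis Set. SAP 1 records that the sponsor discontinued the study without opening phase 2.

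**The concern.** Stopping a drug and leaving a study are different events. A plan that estimates PFS and OS needs subjects to stay under observation after the first. By using nearly the same list for both, 3.5 lets a site end follow-up at the very events that mark a change in prognosis.

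Two separate effects are at stake. A subject removed at progression contributes nothing further to OS and would be censored when the risk of death has probably risen. A subject removed for toxicity, intercurrent illness, non-compliance, a protocol deviation or at the investigator's discretion, before progression, would be censored for PFS at the last adequate assessment. Kaplan-Meier estimation assumes that those censored have the same later risk as those who stay. A removal rule tied to outcome or tolerability puts that assumption in doubt.

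**Working it through.** **1. The two lists.** Section 3.4 has 10 reasons and 3.5 has 11. Nine are common to both: progression, death, investigator discretion, non-compliance, important protocol deviation, loss to follow-up, study termination, intercurrent illness and unacceptable toxicity. The tenth reason in 3.4, the subject's decision, becomes withdrawal of consent in 3.5, which also adds subjects never dosed (9 + 2 = 11). Of the nine, death, loss to follow-up and study termination do end follow-up. The other 9 − 3 = 6 need not.

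**2. Those six against the follow-up sections.**

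| Reason in 3.5 | Survival follow-up (3.3, 6.7) | Scans (6.10) | Censors OS | Censors PFS |
|---|---|---|---|---|
| Progression | conflict | none: scans end at progression | yes | no: progression is the event (SAP Table 6-1) |
| Toxicity, investigator discretion, non-compliance, deviation, intercurrent illness, before progression | conflict | conflict | yes | yes, at last adequate assessment (SAP 6.1.1) |

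SAP 6.2.1 names only subjects lost to follow-up or alive at study end for OS censoring, at the last date known alive. A removed subject with no later contact would be handled the same way.

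**3. The plan's own figure.** Protocol 8.9 says that more than 10 non-progressors of 20 put the lower 90% bound above 30%. The exact two-sided 90% interval for 11/20 is 34.7% to 74.1%, so the figure reproduces. It presumes a known Week 24 status for all 20. The plan gives no rate of removal or dropout.

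**4. Ceiling on removals at progression.** Section 8.9 expects a rate above 30% and considers a true rate above 50%. Taking 50% and 30% as assumed values: 20 × (1 − 0.50) = 10 and 20 × (1 − 0.30) = 14 subjects per group without success at Week 24. This counts PSA-only progressors, who may stay on drug under 3.3, and deaths, which are already OS events. It is a ceiling, not an expected number.

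**5. Direction of bias, by illustration.** Except for the median time to progression, the inputs below are assumptions.

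*OS at 48 weeks* (48 × 7 / 30.4375 = 11.04 months). Median time to progression is 3.6 to 6.6 months (Protocol 1.3). Assumed: death hazard h = 0.01 per month before progression and median survival after progression of 9 to 18 months. With λ = ln 2 / (median time to progression) and μ = ln 2 / (median survival after progression):

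- P0(t) = exp(−(λ + h)t), alive without progression.
- P1(t) = λ / (λ + h − μ) × [exp(−μt) − exp(−(λ + h)t)], alive after progression.
- True OS = P0 + P1. For 3.6 and 9 months: 0.107 + 1.534 × (0.427 − 0.107) = 0.598. For 6.6 and 18 months: 0.281 + 1.373 × (0.654 − 0.281) = 0.793.
- If a share q of progressors is removed at progression, Kaplan-Meier follows the hazard [hP0 + (1 − q)μP1] / [P0 + (1 − q)P1].

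| Medians (months): to progression, then to death | Truth | q = 25% | q = 50% | q = 100% |
|---|---|---|---|---|
| 3.6, 9 | 59.8% | 62.4% | 66.3% | 89.5% |
| 6.6, 9 | 68.5% | 71.5% | 75.4% | 89.6% |
| 6.6, 18 | 79.2% | 80.6% | 82.6% | 89.6% |

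(These rows are simulated values; the formula agrees to within 0.1 point.) At q = 100% the curve reflects only deaths before progression, exp(−0.01 × 11.04) = 0.895, whatever the truth.

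*PFS at Week 24*, scans at Weeks 12 and 24. A share d is removed before Week 12, with progression hazard ratio HR relative to those retained. If x is the Week 24 rate in those retained, truth = (1 − d)x + d·x^HR and Kaplan-Meier estimates x.

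- HR = 1: x equals the truth; no bias.
- HR = 2, d = 30%, truth 30%: 0.7x + 0.3x² = 0.30 gives x = 0.370, 7 points too high.
- HR = 1.5, d = 10%, truth 30%, with removal after Week 12 instead: 30.6%, under 1 point too high.

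**6. Phase 1b.** Section 6.10 makes no phase 1b exception, yet 6.6 and footnote 18 end phase 1b at 30 days. A subject who stops without progression therefore has no planned visit for the later scans. OS at 24 and 48 weeks is planned for subjects whose survival is not followed beyond that visit, although 3.3 says that subjects are followed for survival.

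**The case against.** The best defence is that 3.5 only permits removal, while the survival rules in 3.3, 6.6 and 6.7 are written as requirements. Section 6.10 asks for effort rather than certainty, and it has its own exit where continued scanning is not possible or not acceptable to the subject or investigator. Sections 6.6 and 6.7 still seek later therapy and the progression date, if known, for subjects who came off for other reasons; 6.7 does so even for those who discontinued the study. On this reading 3.5 lists permitted exits and 6.10 states the effort expected.

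Most of this stands, and it limits what can be claimed. A reader might infer that any site following 3.5 ends both kinds of follow-up, or that only 6 to 10 of 20 subjects would remain under OS follow-up. The documents support neither: removal is optional, and the 10 to 14 is a ceiling. A reader might also infer that both curves are biased upward. For PFS that requires higher later risk in those removed; at equal risk there is none. Removal at progression leaves PFS untouched.

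The defence does not remove the contradiction. Section 3.5 carries none of the condition in 6.10 that every effort be made first, and it leaves the choice of who departs to the site. It is also true that OS is a phase 2 endpoint, that phase 2 never opened, and that rewriting 3.5 would not lengthen phase 1b follow-up, which 6.6 ends regardless.

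**Conclusion.** The point holds as a conflict between sections. Section 3.5 allows loss of follow-up for six reasons that need not end it, against 3.3, 6.7 and 6.10. If used, it would censor OS at progression and PFS at toxicity or similar removals.

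No size of bias can be stated from the documents, which give no removal rate, hazard ratio or survival after progression. Under the assumptions above, 48-week OS is 1 to 3 points too high if a quarter of progressors are removed and 3 to 7 if half are. Week 24 PFS is about 1 to 7 points too high with 10% to 30% removed at hazard ratios of 1.5 to 2. These figures show direction and sensitivity; they are not estimates for this trial.

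A reader might conclude that OS results were damaged by 3.5. The documents do not support that: the consequence for OS belongs to a phase that never opened. For the phase 1b data analysed, the live problem is 6.6 and footnote 18 against 6.10 and against the 24- and 48-week estimates in the SAP. This should be fixed, but it is not a fatal flaw.

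**What to change.** - Limit 3.5 to death, withdrawal of consent, loss to follow-up, study termination and subjects never dosed. State that the other reasons in 3.4 end study drug only, and that follow-up under 6.7 and 6.10 continues. The drug-stopping criteria in 3.4 need no change for this purpose.
- Reconcile 6.6 and footnote 18 with 6.10 for phase 1b subjects who stop without progression.
- In the report, show subjects who left without progression or death, by reason, beside the PFS and OS results. SAP 4.1 already tabulates study discontinuation by reason, so this needs only a cross-classification.

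The cost is mainly wording. The phase 2 calls and scans are already planned; only the phase 1b reconciliation could add scans. With phase 1b treatment and safety visits complete, the reporting step is the part that can still help the existing data.

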## 4. SUBJECT POPULATION

### 4.1. Number of Subjects and Subject Selection

Up to 72 subjects who meet the eligibility criteria will be enrolled in the phase 1b dose escalation portion of the study.

Up to 60 subjects who meet the eligibility criteria will be enrolled in the phase 2 dose expansion portion of the study.

### 4.2. Inclusion Criteria

Subjects must meet all of the following inclusion criteria to be eligible for participation in this study.

- 1) Male  $\geq$ 18 years of age
- 2) Histologically or cytologically confirmed prostate cancer (subjects with primary neuroendocrine carcinoma of prostate are excluded)
  - Phase 1b Monotherapy Escalation: Subjects must have documented progressive disease by meeting at least one of the PCWG2 criteria ([Appendix 4](#)) despite treatment with abiraterone and/or enzalutamide
  - Phase 1b Combination Therapy Dose Escalation **and** Phase 2 Combination Dose Expansion (Group 2): Subjects must have documented progressive disease by meeting at least one of the PCWG2 criteria, despite treatment with abiraterone. They may **not** have received prior enzalutamide or chemotherapy for mCRPC
  - Phase 2 Monotherapy Dose Expansion (Group 1): Subjects must have documented progressive disease by meeting at least one of the PCWG2 criteria, despite treatment with enzalutamide. They may have received prior abiraterone, but not prior chemotherapy, for mCRPC
  - Phase 2 Combination Therapy Dose Expansion (Group 3): Subjects must have documented progressive disease by meeting the PCWG2 criteria for PSA progression, but not radiographic progression, despite treatment with enzalutamide. They may have received prior abiraterone, but not prior chemotherapy, for mCRPC (similar to Group 1); however, they must also have been on continuous enzalutamide therapy for at least 12 weeks days prior to Cycle 1, Day 1.
- 3) Castration-resistant disease defined as ongoing androgen deprivation therapy with GnRH analogue or bilateral orchiectomy and serum testosterone level  $\leq$  1.73 nmol/L (50 ng/dL) at screening visit. Subjects who have not had a bilateral orchiectomy must have a plan to maintain effective GnRH-analogue therapy for the duration of the trial.

- 4) Metastatic disease documented by bone lesions on bone scan or by measurable soft tissue disease by CT/MRI. Patients whose disease spread is limited to regional pelvic lymph nodes are not eligible
- 5) All acute toxic effects of any prior antitumor therapy resolved to Grade  $\leq 1$  before the start of study drug dosing (with the exception of alopecia [Grade 1 or 2 permitted] and neurotoxicity [Grade 1 or 2 permitted])
- 6) Eastern Cooperative Oncology Group (ECOG) Performance Status of  $\leq 1$
- 7) Life expectancy of  $\geq 3$  months, in the opinion of the Investigator
- 8) Adequate organ function defined as follows:
  - a) Hematologic: Platelets  $\geq 100 \times 10^9/L$ ; Hemoglobin  $\geq 9.0 \text{ g/dL}$ ; ANC  $\geq 1.5 \times 10^9/L$  (without platelet transfusion or any growth factors within previous 7 days of the hematologic laboratory values obtained at screening visit)
  - b) Hepatic: Aspartate transaminase (AST) / Alanine transaminase (ALT)  $\leq 2.5 \times$  upper limit of normal (ULN) (if liver metastases are present,  $\leq 5 \times$  ULN); total or conjugated bilirubin  $\leq 1.5 \times$  ULN
  - c) Renal: Serum Creatinine  $\leq 1.5 \times$  ULN or creatinine clearance (CrCl)  $\geq 60 \text{ mL/min}$  as calculated by the Cockroft-Gault method
- 9) Coagulation: International Normalized Ratio (INR)  $\leq 1.2$
- 10) Male subjects of childbearing potential who engage in heterosexual intercourse must agree to use protocol-specified method(s) of contraception as described in [Appendix 7](#) and refrain from sperm donation for at least 90 days
- 11) Able and willing to provide written informed consent to participate in the study

